### **8.3.5. Clinical safety laboratory tests**

- See Section [10.2](#) for the list of clinical laboratory tests to be performed and the SoA (Section [1.3](#)).
- The investigator must review the laboratory results, document this review, and record any clinically significant changes occurring during the study as an AE. The laboratory results must be retained with source documents.

- Abnormal laboratory findings associated with the underlying disease are not considered clinically significant unless judged by the investigator to be more severe than expected for the participant's condition.
- All laboratory tests with values considered clinically significantly abnormal during participation in the study should be repeated until the values return to normal or baseline or are no longer considered clinically significant by the investigator or medical monitor.
  - In the absence of a diagnosis, abnormal laboratory findings assessments or other abnormal results the investigator considers clinically significant will be recorded as an AE or SAE, if they meet the definition of an AE or SAE (refer to Sections 10.3.1 and 10.3.2).
  - If clinically significant values do not return to normal/baseline within a period of time judged reasonable by the investigator, the etiology should be identified, and the sponsor notified.
  - If laboratory values from non-protocol-specified laboratory tests performed at the institution's local laboratory require a change in participant management or are considered clinically significant by the investigator (e.g., SAE or AE), then the results must be recorded.

### **8.3.6. Pregnancy testing**

- For women of childbearing potential: only women with negative pregnancy test result at the screening visit (in Phase 1) and at Visit 1 (in Phase 1 and Phase 2) will be included in the study. The study intervention may only be administered if the pregnancy test result is negative at Visit 1 (Day 1, both in Phase 1 and 2). Refer to Section 10.4.1.1 for definition of women of childbearing potential.
- Female participants of childbearing potential must perform a urine pregnancy test before the administration of any dose of study intervention. If time allows, serum pregnancy test can be done as per local requirements. Pregnancy testing must be done even if the participant is menstruating at the time of the study visit. The study intervention may only be administered if the pregnancy test is negative.
- Refer to Section 8.4.6 for the information on study continuation for participants who become pregnant during the study.

### **8.3.7. Study holding rules, safety monitoring committee**

#### **8.3.7.1. Safety monitoring**

Participant safety will be continuously monitored by the medical monitor, designated Safety Lead (or delegate) and **SRT**, throughout the study. Pertinent findings and conclusions are shared with the product's **SRT** for review of the overall benefit-risk profile of the product.

The **SRT** will oversee the unblinded safety monitoring in Phase 1 and blinded safety monitoring in Phase 2 whereas the iSRC will oversee the unblinded safety monitoring in Phase 2. Refer to Section [10.1.6](#) for the **SRT** and iSRC composition and role.

Safety monitoring for Phase 1 and Phase 2 participants is specified in SoA (Section [1.3](#)), [Figure 1](#) and [Figure 2](#), and the safety endpoints are presented in Section [3](#).

Safety assessments for Phase 1 and Phase 2 participants are listed in Section [8.3](#). Study holding rules are listed in Section [8.3.7.1.2](#). Additional safety assessments for Phase 1 participants are listed in Section [10.2](#).

#### **8.3.7.1.1. Phase 1**

Early participants in each group in Phase 1 will be referred to as ‘sentinel participants’. Enrollment and dosing of sentinel and non-sentinel participants will be managed as described below.

- Sentinel participants will be the first 5 participants to be enrolled and dosed in each group.
- On a per site level, sentinel participants will be dosed with an interval of at least 60 minutes between them. On a per site level, a maximum of 7 sentinel participants will be dosed per day and across sites, a maximum of 20 sentinel participants will be dosed per day. All sentinel participants will be observed on site for a minimum of 60 minutes after dosing.
- A safety follow up contact (Contact 1) for all sentinel participants will be performed approximately 20 hours post-dosing.
- After at least 7 days (Day 8) of follow up of sentinel participants, a **SRT** meeting will occur where all available safety data will be reviewed. The **SRT** will decide for each group whether to allow the dosing of non-sentinel participants. The investigator is not permitted to start dosing the non-sentinel participants prior to receipt of the **SRT** meeting outcome. However, screening procedures for non-sentinel participants may be performed prior to receipt of the **SRT** meeting outcome.
- For groups obtaining a favorable decision from the **SRT**, non-sentinel participants can be dosed (unless a holding rule is met). All participants will be observed on site for a minimum of 60 minutes after dosing.
- On a per site level, a maximum of 15 participants will be dosed per day.
- After at least 28 days (Day 29) of follow up of all participants, a **SRT** meeting will occur where all available safety data will be reviewed. The **SRT** will evaluate the overall safety profile for each group and provide a summary to the iDRC (refer to Section [4.3.2](#) for dose selection for Phase 2).
- In addition to the scheduled meetings above, the **SRT** will periodically evaluate the safety data as it becomes available, during the enrollment and follow up period.
- If any safety concerns are identified outside of scheduled **SRT** meetings, an ad-hoc **SRT** meeting will occur, during the enrollment and follow up periods.

Refer to Section 8.3.7.1.2 for Phase 1 holding rules.

#### **8.3.7.1.2. Phase 2 (YA groups)**

In Phase 2, enrollment and dosing of YA participants will be performed as described below.

- Participants in all groups can be enrolled and dosed without restrictions (unless a holding rule is met). All participants will be observed on site for a minimum of 30 minutes after dosing.
- The **SRT** and iSRC will periodically evaluate the safety data as it becomes available, during enrollment and follow up.
- If any safety concerns are identified outside of scheduled **SRT** and iSRC meetings, ad-hoc meetings will occur, during the enrollment and follow up periods.

Refer to Section 8.3.7.2 for Phase 2 holding rules.

#### **8.3.7.1.3. Phase 2 (OA groups)**

In Phase 2, enrollment and dosing of OA participants will be performed as described below. Early participants in each group will be referred to as 'sentinel participants'.

- Sentinel participants will be the first 5 participants to be enrolled and dosed in each group.
- On a per site level, sentinel participants will be dosed with an interval of at least 60 minutes between them. On a per site level, a maximum of 7 sentinel participants will be dosed per day and across sites, a maximum of 20 sentinel participants will be dosed per day. All sentinel participants will be observed on site for a minimum of 60 minutes after dosing.
- A safety follow up contact (Contact 1) for all sentinel participants will be performed approximately 20 hours post-dosing.
- After at least 7 days (Day 8) of follow up of sentinel participants, a iSRC meeting will occur where all available safety data will be reviewed. The iSRC will decide for each group whether to allow the dosing of non-sentinel participants. The investigator is not permitted to start dosing the non-sentinel participants prior to receipt of the iSRC meeting outcome.
- For groups obtaining a favorable decision from the iSRC, non-sentinel participants can be dosed (unless a holding rule is met). All non-sentinel participants will be observed on site for a minimum of 60 minutes after dosing.
- On a per site level, a maximum of 15 participants will be dosed per day.
- In addition to the scheduled meeting above, the iSRC will periodically evaluate the safety data as it becomes available, during the enrollment and follow up period.
- If any safety concerns are identified outside of scheduled iSRC meetings, an ad-hoc iSRC meeting will occur, during the enrollment and follow up periods.

Refer to Section 8.3.7.2 for Phase 2 holding rules.

### 8.3.7.2. Study holding rules

The safety holding rules for Phase 1 and Phase 2, are defined in the **Table 13 and Table 14, respectively**. Holding rules 1a-f will be assessed by the investigator on a continuous basis. Holding rules 2a and 2b will be assessed by the **SRT** in Phase 1 and iSRC in Phase 2 during the safety evaluations of the data. Meeting any of these holding rules will trigger a hold of study intervention administration irrespective of number of participants enrolled and/or timing of the event, for all the study groups.

Of note, no formal holding rules will be applied for other reactogenicity and safety data, such as missed visits due to study intervention-related AEs, Grade 1 and Grade 2 solicited unsolicited AEs in the 7-day follow up period (Day 1 to Day 7) and unsolicited AEs collected from Day 8 to Day 28 after study intervention administration. However, if available, these data will also be reviewed by the **SRT/iSRC** to allow an overall assessment of the benefit/risk ratio of study intervention administration, for each group.

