##### **4.2.1. Rationale for study design of Phase 1**

Phase 1 will assess the reactogenicity, safety and immunogenicity of 12 different formulations and 1 active control to CCI [REDACTED]  
[REDACTED]  
[REDACTED]  
[REDACTED]  
[REDACTED]  
[REDACTED]  
[REDACTED]

The specific aims for Phase 1 (in YAs only) are:  
CCI [REDACTED]

To minimize the number of study groups and number of healthy participants exposed to suboptimal investigational study intervention formulations, the aims of Phase 1 will be investigated using both CCI [REDACTED]  
[REDACTED]

[REDACTED] In addition to addressing the specific aims above, this design will CCI [REDACTED]  
[REDACTED]  
[REDACTED]  
[REDACTED]

CCI

The Phase 1 part will be conducted in YAs only as the pattern (in contrast to the magnitude) of immune responses against subtype A and B lineage strains observed in CCI was comparable between YAs and OAs (refer to IB for details). The findings in Phase 1 for YAs will therefore be applied to both YA and OA groups in Phase 2.

In Phase 1, all study groups will be enrolled in parallel. Given the careful dose escalation conducted in the FLU SV mRNA-003 (217895) and CV2 SARS-COV2-012 BST (218595) studies and the total dose in all study groups will remain below the maximum tolerated dose identified in these studies (refer to Section 4.3.1 for details on dose justification in Phase 1), employing parallel enrolment is considered appropriate.

Comprehensive safety monitoring will be carried out to ensure the safety and wellbeing of the participants (refer to Section 8.3.7 for details). The safety monitoring in Phase 1 includes, but not limited to (1) screening visit, (2) safety laboratory assessment at screening, Day 1, Day 8 and Day 29, (3) inclusion of sentinel participants and review of safety data prior to dosing non-sentinel participants, (4) per site, an interval of at least 60 minutes between dosing of sentinel participants, (5) all participants will be observed on site for a minimum of 60 minutes after dosing, (6) study holding rules, (7) per site, limitation of maximum number of participants dosed per day, (8) across sites, limitation of maximum number of sentinel participants dosed per day and (9) unblinded review of safety data by *SRT*.

#### 4.2.2. Rationale for study design of Phase 2

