**Table 13 Study holding rules for Phase 1**

Holding rule	Events, per dose and per individual study group	Number of participants to pause dosing in all groups, pending further evaluation by the SRT
1a	Death or any life-threatening SAE regardless of causality	≥1
1b	Any non-life-threatening SAE that cannot reasonably be attributed to a cause other than study intervention administration as per Investigator or Sponsor assessment	≥1
1c	Any withdrawal from the study (by investigator or participant request) due to a Grade 3 AE that cannot reasonably be attributed to a cause other than study intervention administration	≥1
1d	Necrosis at the injection site	≥1
1e	Confirmed myocarditis or pericarditis events not clearly attributable to any cause other than study vaccine	≥1
1f	Laryngospasm, bronchospasm, or anaphylaxis within 24 hours after administration of study intervention	≥1
2a	Maximum number of participants with the same Grade 3 solicited local or systemic AE in an investigational vaccine group, with onset within the 7-day (Day 1-7) post-dosing period	≥2
2b	Maximum number of participants with the same or similar Grade 3 related unsolicited AE in an investigational vaccine group, including events with an identical MedDRA High Level Term and events assessed as clinically similar. Includes any Grade 3 or above laboratory abnormalities* of clinical relevance, symptomatic or not, as determined by the investigator	≥2

\* Grading of laboratory parameters will be based on the FDA Guidance for Industry "Toxicity Grading Scale for Healthy Adult and Adolescent Volunteers Enrolled in Preventive Vaccine Clinical Trials". N/A: not applicable

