**Table 14 Study holding rules for Phase 2**

Holding rule	Events, per dose and per individual study group	Number of participants to pause dosing in all groups, pending further evaluation by the iSRC
1a	Death or any life-threatening SAE regardless of causality	<math>\geq 1</math>
1b	Any non-life-threatening SAE that cannot reasonably be attributed to a cause other than study intervention administration as per Investigator or Sponsor assessment	<math>\geq 1</math>
1c	Necrosis at the injection site	<math>\geq 1</math>
1d	Confirmed myocarditis or pericarditis events not clearly attributable to any cause other than study vaccine	<math>\geq 1</math>
1e	Laryngospasm, bronchospasm, or anaphylaxis within 24 hours after administration of study intervention	<math>\geq 1</math>
2a	Maximum number of participants with the same Grade 3 solicited local or systemic AE (same solicited AE lasting 2 consecutive days [48 hours] or more as grade 3)* in an investigational vaccine group, with onset within the 7-day (Day 1-7) post-dosing period	<math>\geq 5\% \text{ (and } \geq 2\text{)}</math>
2b	Maximum number of participants with the same or similar Grade 3 related unsolicited AE in an investigational vaccine group, including events with an identical MedDRA High Level Term and events assessed as clinically similar. Includes any Grade 3	<math>\geq 5\% \text{ (and } \geq 2\text{)}</math>

\* E.g., 2 cases of grade 3 fever occurring 2 consecutive days in 2 participants in the same group

Refer to Section 4.3 for details on selection of doses for further assessment for the next phase of the study.

If a holding rule is met, the investigator must suspend administration of the study intervention and inform GSK immediately (e.g., holding rules 1a-f). Refer to [Table 18](#) for contact information.

The following communication sequence must be followed:

- The concerned site staff has to put study intervention administration on hold.
- The concerned site staff must immediately inform their local GSK contact defined in the [Table 18](#).
- GSKs local medical contact will inform the other sites of their country and the study Clinical Lead. GSK will put the randomization in SBIR on hold.

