- The study Clinical Lead will ensure that all local medical contacts in all study countries are notified.
- All informed site staff will confirm to their local contact that action has been taken providing appropriate documentation to GSK.
- GSK will further evaluate the case with the **SRT** and GSK Global Safety Board and will take the decision to stop or to restart the study intervention administration. All site staff will be informed about that final decision by their local GSK contact.

GSK will inform the investigator if holding rules 2a *or* b are met or if a safety signal is observed during the safety evaluation by the **SRT**/iSRC.

- GSK will put the randomization in SBIR on hold.
- The study Clinical Lead will ensure that all local medical contacts in all study countries are notified upon meeting holding rules 2a-2b.
- Local medical contacts will inform all the sites of their country that a holding rule is met. Following this notification, the study intervention administration should be put on hold.
- All informed site staff will confirm to their local contact that action has been taken providing appropriate documentation to GSK.
- GSK will further evaluate the case with the **SRT**, iSRC and GSK Global Safety Board and will take the decision to stop or to restart the study intervention administration. All site staff will be informed about that final decision by their local GSK contact.
- In case of favorable outcome of the safety evaluations, randomization in SBIR will be re-launched allowing the investigators to restart enrollment and dosing of the remaining participants in the study.

Refer to **SRT** framework, iSRC charter or relevant procedure for details on communication regarding holding rules.

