##### **8.4.1. Time period and frequency for collecting AE, SAE, and other safety information**

All SAEs will be collected from the day of study intervention administration (Day 1) until LSLV (Day 183) at the time points specified in the SoA. SAEs assessed as related to study participation (e.g., study intervention, protocol-mandated procedures, invasive tests, or change in existing therapy) or related to a GSK product (non-IMP) will be recorded from the time a participant consents to participate in the study.

All AEs will be collected from the start of study intervention until Day 7 (for solicited events) or Day 28 (for unsolicited events) at the timepoints specified in the SoA.

Medical occurrences that begin before the start of study intervention but after obtaining informed consent will be recorded as medical history/current medical conditions, not as AEs.

Complete list of safety events to be collected in this study and the timeframes for their collection and reporting are provided in [Table 15](#).

***Investigators are not obligated to actively seek information on AEs or SAEs after conclusion of the study participation. However, if the investigator learns of any SAE, including a death, after a participant has been discharged from the study, the investigator must record it in the medical records. If the investigator considers the event to be reasonably related to the study intervention or study participation, the investigator must promptly notify the sponsor.***

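### The note in Protocol 8.3.7.2 exempts all Day 8-28 unsolicited AEs from the holding rules, which conflicts with rule 2b as tabulated; the note should be reworded

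*Protocol*

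**What the plan says.** Protocol 8.3.7.2 has two consecutive paragraphs on what triggers a hold.

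- The first says that meeting any rule stops dosing in all groups, "irrespective of number of participants enrolled and/or timing of the event".
- The second, a note, says that "no formal holding rules will be applied for other reactogenicity and safety data". Its examples include Grade 1 and Grade 2 events in Day 1-7 and "unsolicited AEs collected from Day 8 to Day 28 after study intervention administration". The grade limit belongs to the Day 1-7 item; the Day 8-28 item has no limit. The note adds that these data will still be reviewed by the SRT/iSRC if available.

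Rule 2b covers the "same or similar Grade 3 related unsolicited AE in an investigational vaccine group". The threshold is at least 2 participants in Phase 1 (Table 13) and at least 5%, and at least 2, in Phase 2 (Table 14). No onset window is given. Rule 2a, directly above it, is limited to onset in Day 1-7. In Phase 1, rule 2b also reaches laboratory findings: "Includes any Grade 3 or above laboratory abnormalities".

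SAP 4.5.1 repeats the sentence on timing, omits the note, and reproduces rule 2b without a window in Tables 5 and 6. Protocol 8.4.1 has unsolicited AEs collected to Day 28.

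**The concern.** A related Grade 3 unsolicited AE starting on, say, Day 15 counts toward 2b under the tables and is exempt under the note. Both texts are in the same protocol section, and nothing says which prevails. The iSRC assesses 2b in Phase 2 and would be working from both.

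Rule 2b is a numeric trigger that pauses dosing in every group. If the note is followed, a cluster of late related Grade 3 events no longer stops dosing by count and depends on the committee calling a signal. Followed to the letter, the note goes further. Protocol 10.3.4 defines unsolicited AEs as including serious ones, so SAEs in Day 8-28 would also fall outside rules 1a and 1b.

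**Working it through.** The documents give no operating characteristic for rule 2b, so there is no stated figure to reproduce. The check is textual first, then an illustration of size.

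**Which text governs?**

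1. *Window wording.* Rule 2a has an onset window and 2b does not, so the drafters wrote a window where they wanted one.
2. *Timing sentence.* The first paragraph of 8.3.7.2 and SAP 4.5.1 both apply the rules irrespective of event timing.
3. *Serious events.* The note, read literally, would exempt a life-threatening SAE on Day 10, which rule 1a stops on at one case. That cannot be intended.
4. *Phase 1 laboratory clause.* Protocol 4.2.1 lists "safety laboratory assessment at screening, Day 1, Day 8 and Day 29". Table 3 allows Visit 2 at 6-8 days after Visit 1 (Day 7-9) and Visit 3 at 28-35 days (Day 29-36). If 2b stopped at Day 7, only a Visit 2 sample drawn a day early could count, and the clause would be almost empty.
5. *SAP.* It carries the tables and the timing sentence but not the note.

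All five point to late events counting. One caution: in the text available, the Table 14 cell for 2b breaks off before its end. SAP Table 6 gives the Phase 2 rule in full, with no window.

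**Does the reading change a decision?** Take the 5% as a share of those dosed to date (an assumption; the protocol does not name the denominator).

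| Phase 2 group | Cases (late) | All counted | Day 1-7 only |
|---|---|---|---|
| 60 dosed | 4 (2) | 4/60 = 6.7%, hold | 2/60 = 3.3%, no hold |
| 120 dosed | 6 (3) | 6/120 = 5.0%, hold | 3/120 = 2.5%, no hold |

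**How often?** Assumed inputs: 120 per group dosed evenly over 4 or 8 weeks; weekly reviews while the group is still dosing; hold if the count is at least 2 and at least 5% of those dosed; early onsets uniform on Day 1-7 and late onsets on Day 8-28; events counted only after onset; half of onsets late; 40,000 simulated trials per case. The rate is the true 28-day rate of one same or similar related Grade 3 event. Each cell is the chance that the group meets 2b, counting all events versus Day 1-7 only.

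| Rate | 4 weeks | 8 weeks |
|---|---|---|
| 1% | 0.5% vs 0.5% | 1.3% vs 0.7% |
| 2% | 2.7% vs 2.3% | 7.1% vs 3.5% |
| 3% | 6.8% vs 5.3% | 17.0% vs 8.1% |
| 5% | 21.1% vs 15.8% | 44.8% vs 22.0% |

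At 3% with 8 weeks of dosing, the pair is 23.5% vs 17.9% if a quarter of onsets are late and 11.1% vs 1.9% if three quarters are.

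For a single look at a full group of 120 the threshold is 0.05 × 120 = 6, and the exact binomial P(X ≥ 6) with half of onsets late is 15.3% vs 1.0% at 3% and 55.8% vs 8.1% at 5%.

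**The case against.** The best defence rests on the word *other* in the note: it can be read as covering only data that the tables do not already address, in which case nothing conflicts. That reading is sensible and probably what was meant. It does not fully cure the text, because Day 8-28 unsolicited AEs are then named without qualification as an example of such data, and the Grade 1-2 limit does not grammatically reach them.

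The defence is stronger on consequence:

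- The SRT/iSRC still sees Day 8-28 events and can meet ad hoc. Protocol 8.3.7.2 runs the same hold sequence "if a safety signal is observed during the safety evaluation by the" SRT or iSRC, and SAP 4.5.1 likewise stops dosing for a signal.
- Necrosis, confirmed myocarditis or pericarditis, and anaphylaxis each have their own rule that triggers at one case.
- The larger gaps above need a 3-5% rate of one related Grade 3 event with many late onsets. With rare events or fast enrolment the two readings nearly coincide.

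Three stronger readings are not supported:

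- *Late events go unmonitored.* The note itself says that they are reviewed.
- *The SAP disagrees with the protocol on 2b or leaves its tabulation undefined.* The SAP tables match the protocol tables, and as written they count Day 8-28 events.
- *Phase 1 dosing decisions are at risk.* Protocol 2.3.3 refers to Phase 1 interim data to Day 29, so Phase 1 dosing was already past at Amendment 2.

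**Conclusion.** The inconsistency is real and sits in one sentence of Protocol 8.3.7.2. The tables, the timing sentence and the SAP all have late related Grade 3 events counting toward 2b; the note is the outlier and should be corrected. A reader might infer that the sponsor meant to restrict 2b to Day 1-7. The documents do not support that, since the same wording would also disable rules 1a and 1b after Day 7.

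The practical stake is limited to Phase 2 and to one question: does a cluster of late related Grade 3 events trigger a hold by count, or only if the iSRC judges it a signal? Particular case splits give opposite answers (6.7% against 3.3% with 60 dosed). The chance of meeting such a split ranges from negligible to substantial. It rests wholly on assumed event rate, onset split, enrolment speed and review schedule. The correction is worth making because the rule concerns safety and the edit is small, not because a large effect has been shown.

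**What to change.** Reword only the note in Protocol 8.3.7.2, so that it exempts data that meet none of the tabulated rules. For example: *no formal holding rule applies to missed visits due to intervention-related AEs, to Grade 1 and Grade 2 solicited and unsolicited AEs in Day 1-7, or to Day 8-28 unsolicited AEs that do not meet any holding rule in Tables 13 and 14*.

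Leave rule 2b as it stands in Protocol Tables 13 and 14 and SAP Tables 5 and 6. Adding a Day 1-28 onset window there looks tidy but would narrow the rule. MAEs and AESIs are collected to Day 183 (Protocol Tables 5 and 15), and Phase 2 cardiac symptoms prompt work-up up to 6 weeks after dosing (8.3.4). A non-serious related Grade 3 event of that kind starting on Day 35 can count now and would be lost. In Phase 1 such a window would also cut off the Day 29 laboratory sample.

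The cost is one sentence, with no new data and no SAP change. The downside is possibly a few more dosing pauses than if the note were followed literally. At an assumed 3% rate with half of onsets late, that is 6.8 − 5.3 = 1.5 percentage points per group with 4 weeks of dosing and 17.0 − 8.1 = 8.9 points with 8 weeks.
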